6.2 Study participant support

6.3 Payments, rewards, and recognition: We have followed the INVOLVE guidance on renumeration for stakeholders and participants, outlined in the detailed budget and cost justification.

6.4. Taking Informed Consent

Assent and Consent

Following enrolment and assent/consent, participants will be asked to complete a questionnaire assessing relevant demographic information (Laurens et al., 2020) (e.g., age, gender, ethnicity, family circumstances) and brief clinical history information (history of past service use, any comorbid diagnoses etc.).

Engagement process for participants

At the beginning of research engagement, the research study will be explained to potential participants in person, via Teams, or by telephone, depending upon the preference of each participant or appropriateness of setting. For example, most engagement activities with young people will be in person, whereas many meetings with staff will be conducted via Teams as this is generally more convenient for practitioners. Consent (participants aged 16-years-old and over) and assent (participants aged 15-years-old and under, with parental/caregiver consent also required) to participate will be obtained during initial meetings that will take place in each of the homes. Following this, as new staff and young people come into the home environment, assent/consent will be taken at a suitable point, in agreement with the home managers.

Following enrolment, participants will be asked to complete a questionnaire assessing relevant demographic information (Laurens et al., 2020) (e.g., age, gender, ethnicity, family circumstances). Pen portraits for each participating young person will also be developed based on their records held by the care provider (i.e., the placement provider).

Following gaining consent/assent, baseline (T1) data will be collected from all participants. At all research assessments, young people will be asked whether they prefer to speak to the researcher alone or in the presence of their primary caregiver, or another trusted adult (e.g., social worker, mentor, advocate, key worker, etc.). Staff will be asked if they would like to speak with the researcher privately, or with their child present. The same process will be followed at each data collection point (table one).

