- The TIC intervention will be taught to staff, who will be supported in implementation through training, supervision, and support workshops. This process will also help the research team build the implementation toolkit around the intervention as it is used, collecting stories from practice, reflective case examples, and problem/solution-based learning examples.
- An integrity checklist, implemented through peer observation and support from the research team.
- An embedded schema for team formulation meetings and supervision for the frontline staff that will initially be run by members of the research team, learnt by the home staff, and then adopted so it can be continued after the pilot has finished.
- SP and EF are experienced trainers and consultants within children's homes, and will conduct the training, supervision, and team formulation sessions, supported by the RP and, in time, home managers.

Data collection will include:

IRAS ID: 337194 NIHR206567

- Personal demographics of all participants at the start of the study or when a new member of staff or young person joins each home.
- Tabulated data from the monthly routine monitoring data (RMD), which all children's homes routinely collect in relation to child development, educational attainment, incidents of concern, and their wellbeing.
- A TIC conversation tool of 10 implementation domains from Scotland's
 Trauma-informed practice toolkit, conducted with house managers and senior
 staff at the start and end of the study.
- Quantitative data to track children's development and wellbeing at the start, middle and end of the pilot:
- 1. RCADS Self-Reported (8-18 years old)
- 2. RCADS Parent version
- 3. Therapeutic Alliance Scale for Children, Revised (TASC-R)
- 4. Trauma-Informed Care Pen Portrait Template
- 5. Resilience Scale for Care Experienced Young People
- 6. Sense of Community in Adolescents Scale (Chiessi, Cicognani & Sonn, 2010)
- The strengths and difficulties questionnaire (SDQ) will be given to children and their key workers at the beginning and end of the pilot, or when the child leaves the home if before the end of the pilot. This plan has been discussed with stakeholders and appears acceptable.
- Key workers and home managers will keep a fortnightly pen portrait documenting intervention integration, integrity, and implementation, which will be accompanied by supportive Microsoft Teams and in-person supervision with a member of the research team.

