- At the start, middle and end of the pilot, all staff members will be asked to complete the Professional Quality of Life Scale (Geoffrion et al, 2019), and a brief TIC self-assessment reflective exercise, which will be created by the research team during WP1. This process will help us identify any changes and tentatively explore relationships between the implementation of the TIC intervention and compassion satisfaction, burnout, and secondary traumatic stress.
- Spoken narrative data from the children's key workers, designated social
 workers and home managers will be collected every eight weeks to elicit their
 stories and experiences of the intervention.
- Young people from the homes will be invited to feedback events at the start, middle and end of the pilot to share their thoughts and views on the experience of the TIC intervention through semi-structured interviews and/or reflective group discussions, depending upon preference.
- We will also create an anonymous Qualtrics platform for written feedback in case there are points staff and young people do not wish to say aloud or in front of others. A member of the research team will be available to support

engagement with this feedback route and the young people will be able to ask for help from an adult they trust within their home as well.

5 Month 1 2 3 4 6 7 8 9 10 11 12 Data **RMD** TIC implementation domains SDQ Quant CYP measures **ProQOL** TIC self-assessment Staff narratives **CYP** narratives

Table One: Data collection timetable

Setting: Four local authority homes in Salford and two privately run homes in Stockport have elected to collaborate on this project to enhance their service delivery. The initial phases of the EBCD approach and baseline assessments taken at the start of the evaluation will inform interpretations of the findings to support theoretical transferability across a fractured and under-performing sector.

Data analysis

Qualitative data analysis software NVivo will be used to manage qualitative transcribed verbal and text data. We will analyse the data using the same realist logic of analysis as in WP1 and qualitative data will be analysed as set out in WP2. Our analysis will enable us to further refine our understand of the new intervention, which will be captured in a refined programme theory. Additionally, we will use the following forms of reasoning to make sense of the data:

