Sense of Community in The SOC-AS is a psychological tool designed to measure Adolescents Scale (SOCadolescents' perceived sense of belonging, connection, AS; Chiessi et al., 2010) and support within a specific community, such as their school, neighbourhood, or peer group. This scale evaluates how well adolescents feel integrated and valued within their community, which is particularly important during adolescence—a developmental stage where social connections play a key role in emotional well-being and identity formation. This scale is particularly useful in contexts like residential care settings or schools, where fostering a sense of belonging can significantly improve adolescents' wellbeing and engagement. Therapeutic Alliance The TASC-r is a 12-item self-report measure designed to Scale for Children (TASCassess the quality of the therapeutic relationship from r; Creed& Kendall, 2005) the child's perspective. The scale evaluates both positive and negative aspects of the therapeutic alliance, including goal agreement, task collaboration, and emotional bond. This measure is appropriate for the NEST study as it assesses the quality of the therapeutic relationship, which is crucial in traumainformed care settings like residential homes. The NEST Study focuses on creating nurturing environments for young people who have experienced significant trauma, and building a strong therapeutic alliance is essential to fostering a sense of safety, trust, and empowerment-

Quantitative ssessments for residential staff

1. Professional Quality of Life Scale (ProQOL) - 30 items (5-8 minutes)

Informed Assent/Consent for Interviews

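### A key worker may sit in while a child rates the therapeutic relationship, and the protocol neither makes that scale private nor says that presence is recorded

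*Protocol*

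**What the plan says.** The rule is in Protocol section 6.4, under the engagement process for participants. It covers every research assessment and has young people asked "whether they prefer to speak to the researcher alone or in the presence of their primary caregiver, or another trusted adult". The key worker is among the examples given: "another trusted adult (e.g., social worker, mentor, advocate, key worker, etc". The same paragraph applies this process to every data collection point. It exempts no instrument.

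A parallel rule covers staff: "Staff will be asked if they would like to speak with the researcher privately, or with their child present".

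Section 6.4.1 schedules the TASC-r and the Sense of Community in Adolescents Scale (SOC-AS) at months 1, 6 and 12. It describes the TASC-r as a 12-item self-report from the child's point of view and gives this reason for using it: "This measure is appropriate for the NEST study as it assesses the quality of the therapeutic relationship". It does not say which adult the child is to have in mind.

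Section 4 (Workstream 3a) has home staff trained in the intervention and supported to put it into practice, with key workers and managers keeping a fortnightly record of its implementation. The same section provides one confidential route: "We will also create an anonymous Qualtrics platform for written feedback". That route is for free-text comments, not for the scales.

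**The concern.** A child who depends on a carer may find it hard to score that relationship poorly with the carer in the room. The rule allows this on the instrument most exposed to it. The possible companion also belongs to the group delivering the intervention under evaluation.

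The pilot has no control group, so its quantitative evidence is the comparison across start, middle and end. If who is present changes between those points, the effect of presence is mixed with any real change in alliance. The planned regression cannot separate the two if presence was never recorded, and presence at month 1 cannot be reliably recovered later.

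The staff rule raises a different problem. A staff member answering the ProQOL, giving a narrative account or completing a key-worker SDQ with the child there may hold back on burnout, distress or the child's difficulties.

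**Working it through.** The protocol gives no figure on this point, so there is none to reproduce. The check sets the provisions side by side and then asks what presence could do to a level and to a change.

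**Provisions together**

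1. Companion option: all assessments, all waves, key worker a named example (section 6.4).
2. TASC-r: child-reported, months 1, 6 and 12, rated adult not named (section 6.4.1).
3. Delivery: by home staff, key workers included (section 4, Workstream 3a).
4. Private completion of the scales, or a record of who was present: not stated. The anonymous platform covers written feedback only.

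Items 1 to 3 mean that the plan, followed as written, can put a person who delivers the intervention, and who may be the person rated, in the room during the TASC-r. Item 4 means that the protocol states no safeguard for the scales.

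**Effect on scores**

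Let b be the shift in score, in SD units, when such an adult is present, and p the share of children so accompanied. Both are assumptions; the protocol gives neither.

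- Bias in the mean at one wave = b × p.
- Bias in change from month 1 to month 12, with b constant = b × (p12 − p1).

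Taking shares of 20% and 60% purely as an example:

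| b (SD) | Level bias at p = 0.20 | Level bias at p = 0.60 | Change bias, 20% to 60% | Change bias, 60% to 20% | Change bias, p constant |
|---|---|---|---|---|---|
| 0.3 | 0.06 | 0.18 | +0.12 | −0.12 | 0 |
| 0.5 | 0.10 | 0.30 | +0.20 | −0.20 | 0 |
| 0.7 | 0.14 | 0.42 | +0.28 | −0.28 | 0 |

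Milder inputs give less. With b from 0.2 to 0.5 and a 30-point change in share, the bias in change is 0.2 × 0.3 = 0.06 to 0.5 × 0.3 = 0.15 SD, in either direction.

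Levels may therefore be shifted whenever anyone is accompanied. Change is shifted only if p, or b itself, differs between waves. The sign of b is also assumed, since a trusted adult might help a child to disclose.

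These values cannot be set against sampling error. The protocol plans for up to 150 young people but gives no expected number with paired scores and no SD of change.

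**Staff rule**

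It governs what staff say to the researcher. It can reach the ProQOL, staff narratives and the key-worker SDQ. It does not enter a child's TASC-r or SOC-AS score.

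**The case against.** A reader might infer that the rule biases alliance and community scores upward, that the key worker is the person rated, and that presence will grow with trust and be read as improvement. The documents support none of these as fact.

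- The TASC-r description names no adult. That it means the key worker is a reasonable inference, because care and intervention come from home staff, but it remains an inference.
- The SOC-AS is described mainly through school, neighbourhood or peer group, with residential care mentioned as a useful setting. A key worker is not obviously what it rates.
- Nothing in the protocol predicts a rising share of accompanied children. The share could fall as children get to know the researcher, or stay level.
- Being alone is offered every time. The rule is about speaking to the researcher, the TASC-r is self-report, and a companion in the room need not see the answers.
- The stated hypothesis names community cohesion, resilience, wellbeing and attainment but not alliance. No measure is ranked as primary, and quantitative data inform programme theory where relevant.
- Section 8.4 places participant contact under bespoke SOPs, which are not available here and may cover how forms are completed.
- Excluding a chosen key worker may lead the children who rely on that person most to skip the scale.

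These points remove any claim about direction or size and make the SOC-AS the weaker case. They do not remove the rule itself. Section 6.4 sets a permission for all assessments without exception. The anonymous platform shows that the authors saw the difficulty of speaking in front of others but did not extend that protection to the scales. The risk of skipped scales is real and has to be counted as a cost.

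**Conclusion.** The concern holds in a limited form. The protocol permits a caregiver or key worker, possibly the rated adult, to be present for the TASC-r at every wave. It states no private completion and no record of presence. Social-desirability bias in TASC-r levels is plausible; in SOC-AS levels it is less clear. Bias in change is possible in either direction if presence or its effect differs between months 1, 6 and 12, and is zero if both are constant.

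The size is unknown. The range of 0.12 to 0.28 SD, up or down, rests wholly on an assumed lift of 0.3 to 0.7 SD and an assumed 40-point change in share. It shows scale and is not an estimate.

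The child-present option for staff is a separate weakness. A reader might take it as further inflating the child scores; it concerns staff reports only.

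**What to change.** In section 6.4 and the assessment SOP:

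1. Keep the child's right to a companion. Have the TASC-r, and preferably the SOC-AS, self-completed out of sight of home staff, with any help from the researcher, an advocate or another trusted adult who is not home staff.
2. Tell the child that home staff will not see the answers.
3. State in section 6.4.1 which adult the TASC-r refers to. Record at each wave whether it is the same adult.
4. Record at each wave who was present, for use in the regression or a sensitivity summary. Private completion matters more than this record: the choice of companion may itself depend on trust, so later adjustment for presence would be imperfect.
5. Remove the option for staff to report with the child present.

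The cost is SOP and protocol wording plus a small number of recorded fields, best settled before month 1. The downside is that some children who rely on their key worker may skip these scales. Missingness on the TASC-r and SOC-AS should therefore be reported at each wave.

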6.3.1 Additional consent provisions for collection and use of participant data

The consent form used for the study will include optional items of consent related to additional collection and use of participant data. It will be made clear that these additional consent options are non-mandatory and that declining additional consent will not prevent them from taking part.

Based on prior experience of working in this field and anticipated media interest in this study, we will also ask participants aged 16 years and over to separately consider providing consent to be passed information about prospective media opportunities (e.g., radio or TV interviews). This approach will mean that consent for the research study is clearly separate from consent to be contacted about media opportunities, although participants who wish to be contacted will have the choice. In previous studies conducted by the research team, participants were often keen to talk about their experiences within media features, which is why we include this element in the protocol, to offer participants the option.

All participants will also be asked whether they give permission for: 1) some of the assessment to be audio recorded for quality checking and for improving study

procedures and assessments; 2) the recordings to be used for supervision/teaching/training; 3) their anonymised data to be used for secondary analysis research; 4) their anonymised data to be made available for data-sharing with other research teams; 5) being contacted at a later stage for participating in further studies related to this area of research; 6) being contacted at a later stage to receive a summary of the study findings; and 7) having their participation in the study recorded in their clinical notes.

6.3.2 Withdrawal of consent and withdrawal criteria

Participants will be free to withdraw from the study at any time. If a participant chooses to do so before the EBCD final collective child's voice film is made, any data collected will be completely removed from the study, deleted, and not used for analysis or dissemination. Should someone wish to withdraw after the EBCD collective child's voice films are made (both age specific and the final combined age film), will fully anonymise that participant's data either by removing that participant from the films altogether and/or concealing/blurring the person's identity and replacing the persons voice with an actor's voiceover so the participant will be unidentifiable. If a participant is deemed to lose the capacity to assent/consent to research while taking part in the study, the participant will be withdrawn from the study. A participant may be withdrawn if the research team are notified of a significant potential threat to the safety of a member of the research team or if a participant displays aggressive or abusive behaviour towards a member of the team. These decisions would be made in consultation with appropriate clinical colleagues and would occur on a case-by-case basis.

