Young people entering the care system have often experienced multiple traumas and loss. Entering the care system itself can be traumatic as a child is removed from the care of people they know and placed in an unfamiliar and unpredictable environment. Of the 82,000 children in care in England, the 12,898 young people in one of 2,873 children's homes are some of the most vulnerable in society. The number of children's homes has increased each year since 2019, with over a quarter of placements located in Northwest England.

What can be done?

Trauma-informed care is an approach that understands and responds to the impact of trauma for a person. Trauma-informed practice aims to provide physical and emotional safety for both the young person who has experienced trauma and their carers to create opportunities to rebuild a sense of safety, empowerment, and form safe relationships to support a fulfilling future. If children who have experienced many adversities do not experience safety in relationships during youth, the risks of exploitation, revictimization and poor health outcomes remains high. Unfortunately, due to a lack of clinical guidance and governance, there are no agreed standards for delivering trauma-informed care specifically for children's homes. Suitable guidance could be developed through collaboration with young people and stakeholders, leading to a new trauma-informed care resource for use in practice.

What will we do?

In this project, we will co-design and pilot a trauma-informed intervention toolkit across six children's homes in the Northwest. The toolkit will provide clear guidance for staff training, trauma-informed supervision, trauma-aware care, and organisational governance to embed trauma-informed thinking into each element of a home's operations. The project has the potential to enhance service quality and improve outcomes for young people, staff, and care providers.

How will we do it?

Firstly, we will bring together existing information from the evidence base for trauma-informed care for young people to look at what works. Secondly, we will hear stories from experience from young people and staff in the children's homes. Learning from these two activities will help us develop the new trauma-informed

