Facilitators will support engagement with discussions, make notes and feedback to all attendees at the end of the breakout groups. With permission from breakout groups, discussions will also be audio recorded to support notetaking. Notes from discussions, comments posted on the event chatroom or comments offered after the event will be collated and discussed between the event facilitators and the rapid realist review team to identify if there are key areas of divergence and/or agreement with the developing programme theory. This deliberation process will allow us to assess how far and where findings may resonate with group members' diverse experiences and assumptions.

WS1 Output: a realist programme theory of the intersections between TIC, adversity, resilience and residential care, which will iteratively feed into the development of the new intervention in WP2, informing likely key performance indicators.

3.b. Pilot Design (Workstream 2)

Experience Based Co-Design (EBCD) is a participatory action research approach that draws upon creative and inclusive design tools and ways of thinking to bring practitioners and experts-by-experience together to improve quality of care (Donetto et al, 2015). EBCD enables the development of a touchpoint/stimulus film that amplifies the child's voice, enables professionals to view the service through young people's eyes, and stimulates discussion to identify priorities for change and intervention. To achieve this, we will conduct the following 8 stages:

Stage one: Interview 10 young people aged 16-18 from the homes to source stories of their experience. Locations and privacy will be arranged on an individual basis. PPIE suggests mealtimes and private spaces within the homes will be preferred for this age group.

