Stage two: Co-produce 10 x individual case study films with the participants aged 16-18 that will firstly be edited into individual case study films; secondly, into an age specific EBCD collective voice film; finally, it will be integrated into the EBCD collective voice film with all age range data. To do this, participants will have four choices over the level of anonymity they wish to have in the interviews. They can choose: 1) a face to camera filmed interview (participants face and voice are captured), 2) concealed face interview (the participants face will be disguised but the voice will be their own), 3) concealed face and actors voice interview, 4) audio interview only (no filming). If participants change their mind and would like to be anonymised at a later date, this choice can easily be amended during the editing prior to the film being shown. All participants will be given the opportunity to co-create their individual films with the film editor (EC). This is to ensure they are happy with how their experience is portrayed and give them the opportunity to edit out anything they do not want to be shared.

Stage 3: Employ creative methods and research-informed conversations with 10-15 children aged 11-15 in the homes, e.g., photographs, poetry, Lego, modelling clay, and artwork to elicit their experiences. This process will be accompanied by a graphic illustrator to record and theme discussions and outputs into a cohesive visual story, accessible for the children. PPIE suggests mealtimes and facilitated play times within the homes will be preferred for this age group, although 1-2-1 opportunities will also be available. We will then collate, anonymise then edit the young people's data (inclusive of pictures of visual outputs) into an agespecific EBCD collective voice film for participants aged 11-15 years.

- Stage 4: Co-produce the final EBCD film by collating all the filmed data of both age ranges to be integrated into the final EBCD collective child's voice film.

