- Stage 5: Show the films to young people and frontline workers from the homes (N=40). During this we will gather responses from the children through message cards, research-focused conversations over mealtimes, and provide the option of 1-2-1 research conversations with a member of the research team. We will also conduct 1-2-1 interviews with staff and older children where they prefer, to gather a rich understanding of their response to the stimulus film and broader perspectives and analyse all data to formulate an overarching narrative.
- Stage 6: Present the overarching narrative and the findings of WP1 and WP2 through EBCD feedback events in each of the four homes, inviting reflective feedback, which will be audio recorded.
- Stage 7: Collate feedback from the four events into the final emancipatory narrative, which will inform the key components for the intervention.
- Stage 8: Co-ordinate intervention development workshops in the four homes to finalise and name the intervention and draft the initial toolkit, which will be further developed from experience of the pilot in WP3.

The Analysis

- Anonymised verbatim transcripts from participants will be analysed.
- Realist Logic Analysis: Identifying common themes, recommendations, and challenges across the qualitative data will inform further development of the CMOCs and programme theory from WS1. This analysis will highlight key areas for improvement and opportunities for trauma-informed care.
- Stakeholder Interpretation Discussions: Collaboratively interpreting findings
 with stakeholders and discussing potential solutions. Their insights will help
 refine our theory and recommendations to ensure they address user needs.
- **Comparative Analysis**: Comparing findings from the pilot with existing literature will enable us to identify best practices and innovative approaches that could be adapted across other homes for cared for children.

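### Section 6.3.2 lets withdrawal after the films are made be met by concealment alone and promises that the participant cannot then be identified, although the films are shown in the same homes

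*Protocol*

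**What the plan says.** Section 6.3.2 of the protocol treats withdrawal in two ways, divided by the making of the final collective film. Before that point, all of the participant's data are taken out and deleted. After it, the data are to be anonymised "either by removing that participant from the films altogether and/or concealing/blurring the person's identity". The second of these routes also alters the sound of the film, by "replacing the persons voice with an actor's voiceover so the participant will be unidentifiable". The wording sets no condition on that result and does not say whether the participant or the team picks the route.

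Section 8.6 returns to the matter for participants who chose an identifiable filming option. If they withdraw after the final film is made and uploaded, their individual case study film is deleted and taken off the hosting site. For the age-specific and combined films it speaks only of anonymising the data and uploading an amended version.

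Section 3.b (Workstream 2) describes how the films are made and used. Stage two offers 16-18-year-olds four levels of anonymity, the first being "a face to camera filmed interview (participants face and voice are captured" on film. A participant who has second thoughts is told that "this choice can easily be amended during the editing prior to the film being shown". Stage 4 completes the combined film. Stage 5 is then: "Show the films to young people and frontline workers from the homes (N=40" in total).

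**The concern.** The audience for the films is the group best placed to recognise the storyteller: the people who live with the young person and the staff who provide the care. A participant who has appeared with face and voice has been seen by that group once a showing has taken place, and no later edit reverses this. A participant whose face and voice are hidden is still telling a personal story to people who may know it.

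What is at stake is whether agreement to be filmed rests on an accurate account of what withdrawal can achieve, and whether a young person in care who withdraws can count on their material no longer being used. Under the present text, it can stay in circulation in altered form without their having asked for that.

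**Working it through.** The plan states no figure on this point, so the check sets the relevant passages side by side.

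**Inputs**
- Filmed participants aged 16-18: 10 ("Interview 10 young people aged 16-18 from the homes", section 3.b, Stage one). Any of them may choose to be identifiable.
- Contributors aged 11-15: 10 to 15 ("research-informed conversations with 10-15 children aged 11-15 in the homes", Stage 3). Their material is anonymised before it is edited.
- All film contributors: 10 + 10 = 20 to 10 + 15 = 25.
- Planned audience at Stage 5: 40 young people and frontline workers from the homes.
- Home size: not given for the study homes. Section 1 gives only national figures ("the 12,898 young people in one of 2,873 children's homes"), or 12,898 / 2,873 = 4.49 per home. This is context, and the argument does not rest on it.

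**What the text delivers, by time of withdrawal**

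| Withdrawal occurs | Rule | Removal route | Concealment-only route |
|---|---|---|---|
| Before the final film is made | All data deleted (6.3.2) | Not needed | Not offered |
| After it is made, before it is shown | Removal and/or concealment (6.3.2) | Works fully | Story still shown in the homes; teller may be recognised |
| After it is shown | The same rule; 8.6 adds deletion of the individual film | Protects later viewers only | Protects later viewers only in part; earlier viewers have already seen the participant |

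The promise is secure in only one of the four cells that apply to late withdrawal: removal before any showing. In the other three it is broken or in doubt. The last row is not remote, because showing the films in the homes is the purpose of Stage 5.

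**Two further comparisons**
1. Concealment on late withdrawal matches the third anonymity level in Stage two: hidden face and an actor's voice. A young person dealt with in this way is, in the collective film, where a continuing participant who chose that level would be. Their contribution has been disguised, not withdrawn.
2. Staff in these homes know the young people's histories. Section 4 has key workers and home managers keep fortnightly pen portraits, and section 6.4 draws pen portraits of the young people from the provider's own records. A disguised face and voice do not disguise a history to such viewers.

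**The case against.** The strongest reply is that the same sentence in 6.3.2 names complete removal first, so blurring and re-voicing are not the only remedy. That is right. The objection is that the text allows concealment to be enough by itself and leaves open who decides.

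Secondly, the claim can be read as applying only to the amended film, and not as saying that earlier viewers will forget. This is a fair reading and it narrows the fault, but it does not remove it: a concealed story in the amended film can still be recognised by people who know the teller. If the narrower meaning is intended, the protocol should say so.

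Thirdly, there are real safeguards before any showing. Stage two lets participants alter their anonymity level. Section 8.6 adds co-editing of the individual film, a second chance to change that level, the right to cut content, and participants' approval of the films. These reduce the chance of late regret, but none of them covers withdrawal after a showing.

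Some stronger readings are tempting and are not supported. A reader might infer that each home has only one or two storytellers. The size of the study homes is not stated, and the study has six homes while Stages 6 to 8 of Workstream 2 refer to four, so no reliable count per home follows. A reader might also infer a risk of reprisal, or guarded accounts that bias the intervention. Nothing in the protocol shows either, and someone who chose face to camera did not rely on concealment when speaking. Nor can it be said that participants are left uninformed, because the consent materials are not available here.

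**Conclusion.** The point holds in limited form. Section 6.3.2 makes an unconditional promise that its own concealment route, combined with the Stage 5 showings, cannot keep. The failure is clearest for a participant who was filmed openly and withdraws after a showing. It is possible for anyone whose story is recognisable, whenever the film is shown. Section 8.6 does not close the gap, because it does not state removal from the collective films.

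By the planned numbers, at most 10 participants could have been filmed openly, 20 to 25 contribute to the films, and 40 people are due to see them. How many would withdraw late is not given and cannot be estimated from the protocol. No sample size, analysis or outcome measure is touched: this concerns confidentiality and the accuracy of what participants are told. The conclusion assumes only that viewers in the homes know the young people they live or work with, and it does not depend on how small the homes are.

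**What to change.** Amend sections 6.3.2 and 8.6 together so that they give one rule:
- On withdrawal after the films are made, removal from every film (individual, age-specific and combined) is the default. Concealment is used only if the participant asks to stay in on that basis.
- The old version is not shown again until the new cut is in place.
- The claim that the participant cannot be identified is replaced by two statements: that the protection applies to future versions, and that people who have already seen the film, or who know the participant, may still recognise them.
- The consent and assent materials are checked to make sure they say the same.

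The cost is protocol wording, some re-editing and the loss of that participant's film content. Removal is an editing option that the protocol already offers.
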